1 PROTOCOL SUMMARY

1.1 SYNOPSIS

Title	NIcotinamide Riboside in SARS-CoV-2 pAtients for reNAl protection (NIRVANA)			
Study Description	A pilot, double-blind, placebo-controlled, multicenter, interventional clinical trial with oral nicotinamide riboside (NR) 500 mg (versus placebo) twice daily for a total of 10 days in hospitalized participants with COVID-19.			
Objectives	Primary			
	 To determine the effect of nicotinamide riboside (NR) on whole blood NAD+ levels in hospitalized patients with COVID-19 infection and AKI during the 10-day intervention period; To evaluate the safety of NR in patients with COVID-19 infection and AKI during the 10-day intervention period; 			
	Secondary			
	 To determine the effect of NR on changes in area under curve (AUC) serum creatinine from baseline during the 10-day intervention; To determine the effects of NR on serum creatinine AUC, dialysis, and death with an ordinal categorical outcome having four categories (labeled 1, 2, 3, 4), defined as, in order from least to most severe disease, 1. Serum creatinine AUC < median, 2. Serum creatinine AUC ≥ median, 3. Dialysis, 4. Death during the 90d period post randomization; To determine the effect of NR on MAKE (Major Adverse Kidney Events; composite criteria defined as development or progression of chronic kidney disease, the initiation of long-term dialysis, or death from any cause) at 30d and 90d post randomization; To determine the effect of NR on degree of kidney impairment defined with estimated glomerular filtration rate (eGFR) and proteinuria at 30d and 90d post randomization; 			
	Exploratory			
	• To determine the relationship of whole blood NAD+ levels with AUC creatinine and surrogate markers of AKI such as kidney injury molecule- 1 (KIM-1) and neutrophil gelatinase-associated lipocalin (NGAL);			
Endpoints	Primary			
	 Rates of change in whole blood NAD+ level from baseline to day 10 in NR compared to Placebo. Safety of NR in hospitalized patients with COVID-19 and AKI (defined as the occurrence of at least one serious adverse event of grade 3 or higher or the occurrence of thrombocytopenia (>25% decline in blood platelet count from baseline value). 			

	Secondary				
	 Rates of change in AUC serum creatinine benchmarked to baseline from baseline to day 10 in NR compared to Placebo; An ordinal categorical outcome with four categories (labeled 1, 2, 3, 				

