We chose a treatment protocol with NR as a treatment for patients who will be admitted with COVID-19 related illness and develop AKI after admission. Treatment duration will be for 10 days and the primary study endpoint will be the change in whole blood NAD+ from baseline (to 10d, 2d, AUC) in NR group vs placebo group. We will evaluate whole blood NAD+ levels as a marker of efficacy and biological effect of NR based on two recent publications [8, 15]. We evaluated using a marker of efficacy for NR with the whole blood NAD+ based on two recent publications [8, 15]. In a study of healthy overweight subjects 40-60 years of age, Conze et al.

[8] found a 21 µg/ml mean NAD+ difference between patients randomized to 1000 mg NIAGEN[®] versus those randomized to placebo at day 7 (NIAGEN 42 µg/ml, Placebo 21 µg/ml) with a standard deviation of 10 µg/ml and approximately equal baseline means (NIAGEN 21 µg/ml, Placebo 24 µg/ml). Simic et al. [15] assessed a combination of NR with pterostilbene (NRPT) vs placebo in hospitalized patients of age \geq 18 years with AKI and found an 18% increase in whole blood NAD+ within 48h post treatment in the NRPT group, and a 50% reduction from baseline in the placebo group with AKI. With reference to Conze et al. [8] al., this study will achieve >99.9% power for testing H₀:R_{NR} = R_{Placebo} versus Ho: R_{NR} ≠ R_{Placebo} with alpha=0.05, autocorrelation (ρ)=0.5, and n=40 per arm where R_{NR} and R_{Placebo} are the rates of change from baseline to day 10 in the NR and Placebo arms, if the effects observed in this study are the same as those observed by Conze et al. with regard to NAD+. In this setting the effect size is 2.1 [=(42-21)/10] and the minimally detectable effect size is 0.63.

Safety of NR will also be assessed as a primary endpoint in this study. Although NR is generally recognized as safe or GRAS [17] and has been demonstrated to be well-tolerated with mild, if any side effects, reported using variables doses from 100 mg/day up to 2000 mg/day [8, 11, 12] it will be informative to assure that serious adverse events (SAEs) are not increased with NR in patients with COVID-19 infection and AKI.

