 baseline during the 10-day intervention; To determine the effect of NR on serum AUC, dialysis, and death with an ordinal categorical outcome with four categories (labeled 1, 2, 3, 4), defined as, in order from least to most severe disease, 1. Serum creatinine AUC < median, 2. Serum creatinine AUC ≥ median, 3. Dialysis, 4. Death; To evaluate the effect of NR on on MAKE (composite criteria defined as development or progression of chronic kidney disease), the initiation of long-term dialysis, or death from any cause) at 30d and 90d post randomization. To determine the effect of NR on kidney function defined by eGFR and proteinuria at 30d and 90d post randomization. 	 outcome with four categories (labeled 1, 2, 3, 4), defined as, in order from least to most severe disease, 1. Serum creatinine AUC in the first tertile, 2. Serum creatinine AUC in the second tertile, 3. Serum creatinine AUC in the third tertile, 4. Death; Time to first occurrence of MAKE defined as doubling of serum creatinine, the initiation of long-term dialysis, or death from any cause at 30 day and 90 day post randomization; Kidney function defined by estimated glomerular filtration rate (eGFR) and proteinuria at 30d and 90d post randomization. 	 days of intervention and benchmarked to baseline, has been linked to reduced progression of chronic kidney disease (CKD). The ordinal categories address the hierarchy of increase in severity as has been used in recent COVID-19 studies as per the World Health Organization clinical progression scale [57, 58] AKI may progress to CKD which is associated with need for dialysis and increased mortality.
• To determine the relationship of whole blood NAD+ levels with AUC creatinine and surrogate markers of AKI such as kidney injury molecule-1 (KIM-1) and neutrophil gelatinase- associated lipocalin (NGAL);	• Correlations between whole blood NAD+, AUC serum creatinine, and surrogate markers of AKI such KIM1 and NGAL;	 AUC of serum creatinine is a direct assessment of the duration and severity of AKI; KIM-1 and NGAL are promising surrogate urinary biomarkers of AKI however, their clinical utility in COVID-19 patients with AKI is not known;

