5 STUDY POPULATION

5.1 INCLUSION CRITERIA

Inclusion and Exclusion Criteria must be confirmed by a clinician listed on the delegation log. If there is any uncertainty, the site principal investigator will make the decision on whether a potential participant is eligible for study enrollment.

In order to be eligible to participate in this study, an individual must meet all of the following inclusion criteria:

- 1. Provision of signed and dated informed consent form from a participant or legally authorized representative (LAR);
- 2. Male or female, >18 years old;
- 3. Admitted to hospital with a laboratory diagnosis of COVID-19 infection and COVID-19 related illness and evidence of persistent AKI as defined by the Kidney Disease:

Improving Global Outcomes (KDIGO) guidelines during the first 10 days following admission (Table 3);

4. Willing to adhere to the study intervention regimen;

Rationale: Persistent AKI Stage 1 will be defined as absence of recovery from the AKI stage within 24 hrs after receiving standard of care management by the primary provider team. The NIRVANA study team will monitor serum creatinine daily and participants with sustained AKI will proceed to randomization.

Table 3: Staging of AKI by the Kidney Disease: Improving Global Outcomes [72]						
AKI Stage	Serum Creatinine	Urine output				
1	1.5 - 1.9 x baseline	<0.5 mL/kg/h for 6-12 h				
2	2.0 - 2.9 x baseline	$<0.5 \text{ mL/kg/h for} \ge 12 \text{ h}$				
3	3.0 times baseline OR increase in serum	<0.3 mL/kg/h for \geq 24 h OR				
	creatinine \geq 4.0 x baseline OR initiation of	anuria for ≥12 h				
	renal replacement therapy					

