9.4.3 ANALYSIS OF THE SECONDARY ENDPOINT(S)

SECONDARY END POINT: AUC Serum creatinine over 10 days adjusted for baseline serum creatinine

We expect that rate of change in AUC serum creatine will be decreased in the NR group relative to the Placebo group. The null hypothesis to be tested is $H_0:R_{NR}=R_{Placebo}$, where R_{NR} and $R_{Placebo}$ are the rates of change in serum creatinine from baseline to day 10 in the NR and Placebo arms. Serum creatinine will be measured daily in each patient during the first 10 days upon randomization. Serum creatinine AUC will be graphically summarized with spaghetti plots and overlaid line and whisker plots of the mean trajectory for each arm with the whiskers being of length equal to one standard error of the mean. To address non-ignorable missingness due to dialysis, death, or withdrawal of consent, all of which may be considered as informative censoring, the statistical method will be the same as that specified for NAD+. Potential participants who may have severe AKI or advanced CKD will considered with a binary independent variable in the models addressing this condition with corresponding displays of the line and whisker plots by treatment group and summary tables of coefficients, standard errors and p-values. Interactions between this binary variable and treatment will be of interest and will be described.

SECONDARY END POINT: Serum creatinine AUC and ordinal categorical outcome with four categories including dialysis and death

Serum creatinine AUC will be computed using the trapezoidal rule within each patient starting from randomization to day 10, and will be assigned to Category 1 if AUC < median AUC, to Category 2 if AUC \geq median AUC in those who do not experience dialysis and who do not die during the first 10 days of hospitalization. Patients who experience dialysis at any time during the 10 day period will be assigned to the Category 3 and those who die during the first 10 days of hospitalization to Category 4. The null hypothesis is H₀: OR₁=OR₂=OR₃=1, where OR₁, OR₂, and OR₃ are the odds ratios for Categories 1, 2, 3, and 4. If the proportional odds model holds the null hypothesis is H₀:OR=1 where OR is the single odds ratio summarizing the treatment effect. With NR treatment we expect that the odds of Category 1 will be increased, the odds of Category 2, 3, and 4 will be decreased.

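### The four-category creatinine AUC, dialysis and death endpoint has conflicting definitions, and its scoring rule takes AUC from randomization but counts death by days of hospitalization

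*Combined protocol and SAP*

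**What the plan says.** Section 9.4.3 holds the operational rule. For the AUC it states: "Serum creatinine AUC will be computed using the trapezoidal rule within each patient starting from randomization to day 10". Categories 1 and 2 are a split at the median AUC "in those who do not experience dialysis and who do not die during the first 10 days of hospitalization". Dialysis at any time in a 10-day period, whose start is not given, is Category 3. The rule then assigns "those who die during the first 10 days of hospitalization to Category 4".

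Two other current statements of the endpoint differ. The secondary objective in the synopsis (Section 1.1) ends its list with "Death during the 90d period post randomization". The endpoint column of Table 2 (Section 3) lists three AUC tertiles and then death, ending "Serum creatinine AUC in the third tertile, 4. Death", so dialysis has no category.

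On entry, Section 2.1 describes "patients who will be admitted with COVID-19 related illness and develop AKI after admission". Section 5.1 accepts AKI arising in the first 10 days after admission and defines persistent Stage 1 AKI as "absence of recovery from the AKI stage within 24 hrs after receiving standard of care management".

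**The concern.** The definitions describe different outcomes, and nothing says which one governs. The analyst would have to choose between tertiles and a median split, between having a dialysis category and having none, and between a 10-day and a 90-day window.

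Within Section 9.4.3 itself, AUC is tied to randomization and death to hospitalization. If the hospital phrase is programmed as written, a patient randomized some days after admission can die during the 10 study days and still fall outside Category 4. Without dialysis, that patient meets the written condition for one of the two mildest categories.

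The result carries weight. Section 2.1 lets any one secondary outcome at p<0.2 support a later trial, together with no increase in harm and, for Phase III, a significant NAD+ increase. Section 9.4.3 ties further study to p of 0.05 or less on this endpoint.

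**Working it through.** The plan gives no power or sample size for this endpoint, so there is no stated figure to reproduce.

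**1. The definitions side by side**

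| Place | AUC part | Dialysis | Window for death |
|---|---|---|---|
| 1.1, objective | median split | Category 3 | 90 days after randomization (may be meant for the whole outcome) |
| 1.1, endpoint | median split | Category 3 | none stated |
| 3, Table 2, objective | median split | Category 3 | none stated |
| 3, Table 2, endpoint | tertiles | no category | none stated |
| 9.4.3 | median split, randomization to day 10 | Category 3, 10-day period | first 10 days of hospitalization |

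This conflict needs no interpretation of the hospital phrase.

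**2. The literal death window.** Take admission as hospital day 1 and randomization on hospital day E. Study day d is then hospital day E+d-1, which is outside the window when E+d-1 > 10. The number of study days outside is min(E-1, 10):

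- E=1: 0
- E=2: 1
- E=3: 2
- E=5: 4
- E=8: 7
- E=11 or later: 10

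**3. Illustrative counts.** Section 2.2 reports 120 deaths among 1213 comparable patients: 120/1213 = 9.9%, with death dates unknown. The following are assumptions: entry spread evenly over the hospital days shown; 30%, 50% or 100% of deaths in study Days 1-10; deaths spread evenly over those days. Deaths outside the window per 100 = 9.9 x share of deaths in Days 1-10 x mean share of study days outside.

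| Entry on hospital days | Mean share outside | 30% | 50% | 100% |
|---|---|---|---|---|
| 1-3 | 0.10 | 0.3 | 0.5 | 1.0 |
| 1-5 | 0.20 | 0.6 | 1.0 | 2.0 |
| 1-10 | 0.45 | 1.3 | 2.2 | 4.5 |
| 1-12 | 0.542 | 1.6 | 2.7 | 5.4 |

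Each figure is an upper bound for misplacement into Categories 1-2 in its scenario, because dialysed patients go to Category 3. At 9.9% mortality the extremes are 0 per 100 (all enter on hospital day 1) and 9.9 per 100 (all enter on day 11 or later and all deaths fall in study Days 1-10).

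If the 9.9% were 90-day mortality, the choice between a 10-day and a 90-day death window would concern 9.9 x (1-0.3) = 6.9, 9.9 x (1-0.5) = 5.0, or 0 deaths per 100.

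**4. Effect on the odds ratio for a worse category.** This uses an unadjusted cumulative-logit model fitted to expected proportions. Assumptions: 10% dialysed per arm, the same AUC distribution in survivors of both arms, and the pooled median re-cut among everyone left in Categories 1-2.

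*Same misplaced share in both arms (0%, 10%, 20%, 45%), into Category 1:*

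- Death 10% placebo, 5% NR: 0.825, 0.847, 0.870, 0.932. If misplaced into Category 2 instead: 0.825, 0.834, 0.842, 0.864.
- Death 5% placebo, 10% NR: 1.21, 1.18, 1.15, 1.07.
- Equal death rates: 1.00 throughout.

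*Different misplaced share by arm.* Take death at 10% in both arms, with 20% of placebo and 60% of NR deaths misplaced into Category 1. Per 100 patients in each arm, 2 placebo and 6 NR deaths move. Categories 1-2 then hold 80+2 = 82 and 80+6 = 86, or 168 pooled, so Category 1 holds 84. Of these, 84-8 = 76 are survivors, 38 per arm. The cells for Categories 1 to 4 are 40/42/10/8 (placebo) and 44/42/10/4 (NR). The fitted odds ratio is 0.81, although death, dialysis and survivors' AUC are equal. Swapping the arms gives about 1.24.

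**The case against.** The strongest reply is that the hospital phrase simply means the 10 study days. Section 6.4 gives patients discharged before 10 days of hospitalization enough drug to complete 10 days in total, which makes sense only if those are study days. Section 6.1.1 pairs Day 1 to Day 10 with a hospital duration of at least 10 days. Sections 6.1.2 and 6.2.1 use a hospital stay under 10 days in the same way, and Section 8.1 starts its similar phrase at Day 1. The literal rule also defeats itself: for entry on hospital day 11, no death after randomization could reach Category 4. This stands as the probable intent. A reader might infer that the plan means to score late deaths among the mildest outcomes; the documents do not support that.

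It does not fully settle the wording. Section 9.4.3 uses a randomization clock for creatinine, Section 5.1 uses a true admission clock for AKI onset, and no text equates the two. The conflict among definitions remains on any reading of the phrase.

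Three further points against stand in part:

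- Early entry may be common. Section 2.2 speaks of newly admitted patients, and the 24-hour persistence rule is stated for Stage 1 only.
- Even the literal rule does not fix the score. A patient who dies on day 8 has no day-10 AUC, and the choice between a truncated AUC (Section 8.1 computes it cumulatively) and imputation (Section 9.4.1) is not made for this case.
- This is one secondary endpoint in a trial that calls itself exploratory, and MAKE counts deaths to day 90.

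**Conclusion.** The point holds as a conflict among current definitions, together with a scoring rule whose death window does not match its AUC window as written. The hospital-clock mis-scoring follows only from a literal reading.

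Its size cannot be determined, because entry days and death dates are not in the documents. On the stated assumptions it is small with early entry: 0.3 to 1.0 deaths per 100 for entry on hospital days 1-3, and an odds ratio of 0.847 instead of 0.825 when a tenth of deaths are misplaced into Category 1. Larger effects need late entry to be common.

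A reader might infer that the error always dilutes the effect, or that equal death rates rule out a false benefit. Both hold only if the misplaced share is the same in the two arms. If the timing of entry or death differs by arm, the bias can go either way, as the 0.81 shows. Nor do the documents show that such a difference is expected, so a claim of false benefit is not supported either.

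The definitions should be corrected before analysis. The consequence is confined to this endpoint and the two decision rules that use it.

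**What to change.** Use one definition in Section 1.1 (objective and endpoint), Section 3 Table 2 (both columns) and Section 9.4.3: median split of AUC, dialysis, and death, all counted from randomization through study Day 10. Specifically:

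- In Section 9.4.3, replace the hospitalization phrase in both places with study Days 1-10 from randomization, and say that the dialysis period is the same window.
- In the endpoint column of Table 2, replace the tertile categories with the median split and restore the dialysis category.
- In the synopsis objective, remove the 90-day window.

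The number of study days outside the death window is then 0 for every entry day. If 90 days is intended, state in every place whether it applies to death only or to dialysis as well.

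The cost is wording. Section 1.3 already schedules endpoint assessment and mortality on Days 1-10, 30 and 90, so the 10-day definition needs no new visits, data or sample size.

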Missing data can threaten the inferences made about study questions. The study team will make every effort to minimize the impact of missing data, including attempting to obtain final information on participants even if adherence to study procedures is poor or they do not follow the randomized treatment. In cases where missing data is unavoidable, we will use multiple imputation using chained equations to impute outcomes and relevant covariates to mitigate the potential impact of missing data, combining across imputations with Rubin's rules to account for the variability in the imputation procedure [84]. Any data point that appears erroneous or inexplicable based on clinical judgement will be investigated by study staff. If data points are considered to be outliers then sensitivity analyses will be carried out with and without the suspected outlier. Under the missing at random (MAR) assumption the estimates provided by our planned repeated measures statistical models using maximum likelihood estimation will be asymptotically unbiased [85].

All data will be summarized by treatment and clinical site in all randomized participants. Statistical estimates of treatment effects (with 95% confidence intervals, where appropriate), and p-values will be tabulated. All statistical tests will be two-sided with a significance level of 5%. R and/or SAS will be used throughout. Due to the overall exploratory nature of this study corrections for multiple comparisons will not be applied.

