The primary analysis will be based on a cumulative logit model for ordinal data of the primary outcome with terms for treatment, age, gender, clinical site, and baseline serum creatinine. The proportional odds assumption will be tested with a score statistic and empirical logit plots. If the proportional odds assumption is violated then the analysis will be conducted under a partial proportional odds assumption. Under a partial proportional odds assumption, three odds ratios will be estimated; if evidence suggests that the proportional odds assumption holds, a single odds ratio will summarize the treatment effect. In either case, the odds ratio estimate(s), 95% confidence interval(s), and p-value(s) will be reported. Further study will be indicated if the p-value for any treatment effect suggesting benefit in the NR arm is less than or equal to 0.05.

SECONDARY END POINT: Major Adverse Kidney Events (MAKE)

The null hypothesis is H₀:HR=1 where HR is the ratio of the hazard of MAKE with NR treatment to the hazard of MAKE with Placebo treatment. We expect that HR will be less than 1. MAKE is defined as Yes if a doubling of serum creatinine (from baseline), the initiation of long-term dialysis, or death from any cause is observed, and No otherwise. Treatment arms will be compared with regard to the time to the first occurrence of MAKE over the entire duration of the study from baseline to 90 days post-randomization with proportional hazard models of time to MAKE in terms of treatment without and with adjustment for age, race, clinical site, baseline

serum creatine. The coefficients, standard errors and 95% confidence intervals and corresponding hazard ratios will be reported without and with adjustment for covariates. The proportional hazards assumption will be assessed with Schoenfeld residuals and log survival plots. The unadjusted model will be graphically summarized with overlaid Kaplan Meier curves and the p-value for the corresponding log rank test. Covariate interactions with treatment will be of interest and will be explored.

SECONDARY END POINT: Kidney impairment as indicated by eGFR and proteinuria at 30 and 90 days

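### Ordinal endpoint (9.4.3): if the proportional-odds check fails, one treatment odds ratio becomes three and any one favouring NR at p ≤ 0.05 counts; after that switch the false-positive rate favouring NR is about 6–7% instead of 2.5%

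*Combined protocol and SAP*

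**What the plan says.** Section 9.4.3 puts participants into four categories: creatinine AUC below the median, AUC at or above the median, dialysis within 10 days, and death within 10 days. The null is that all three odds ratios equal 1 or, if proportional odds holds, that the single odds ratio equals 1.

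The model is a cumulative logit with treatment, age, gender, site and baseline serum creatinine. On the check, the plan says: "The proportional odds assumption will be tested with a score statistic and empirical logit plots". It gives no threshold and does not restrict the check to treatment. If the assumption holds, "a single odds ratio will summarize the treatment effect". If not: "If the proportional odds assumption is violated then the analysis will be conducted under a partial proportional odds assumption", and "Under a partial proportional odds assumption, three odds ratios will be estimated".

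The decision rule is that further study is indicated if "the p-value for any treatment effect suggesting benefit in the NR arm is less than or equal to 0.05". Section 9.4.1 makes all tests two-sided at 5% and, because the study is exploratory, states that "corrections for multiple comparisons will not be applied".

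**The concern.** Two things do not fit together.

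First, the hypothesis is joint, but after the switch the rule takes the best of three p-values with no adjustment. That is not a 5% test of the stated null.

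Second, the trigger need have nothing to do with treatment. The AUC in 9.4.3 runs from randomization to day 10. It therefore contains the baseline value, and the text for this endpoint does not benchmark it. Baseline creatinine should then separate category 1 from category 2 more sharply than it separates death from the rest. A check across all model terms can fail for that reason alone, and the plan responds by freeing the treatment effect.

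At stake is the error rate of a result that 9.4.3 ties to a recommendation for further study. After the switch, one of the three odds ratios is death against the rest. The 9.9% mortality quoted in section 2.2 (dates of death unknown) would give about 10 deaths in 100 participants, or about five per arm, and possibly fewer by day 10.

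**Working it through.** **The plan's own figure.** The plan states no error rate or power for this endpoint. Its only sample-size figure is for NAD+: at 40 per arm and 80% power, (1.960 + 0.842) × √(2/40) = 0.626, which agrees with the stated minimum detectable effect of 0.63.

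**Inputs from the documents.** 100 randomized 1:1; three sites; two-sided 5%; three cutpoints; no multiplicity correction.

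**Assumed, because not given.** Ten-day dialysis 5–15% and death 5–10% in simulation (3–20% and 2–9.9% in the large-sample calculation); a 5% threshold for the score test; the association of baseline creatinine with AUC.

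**Step 1: error once three odds ratios are tested.** Under the null, the three cumulative-logit treatment estimates are approximately jointly normal. With g the cumulative probability at each cutpoint, the correlation for j < k is √[g_j(1−g_k) / (g_k(1−g_j))].

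Example: dialysis 10%, death 8%, so g = 0.41, 0.82, 0.92.
- r12 = √(0.41 × 0.18 / (0.82 × 0.59)) = 0.39
- r13 = √(0.41 × 0.08 / (0.92 × 0.59)) = 0.25
- r23 = √(0.82 × 0.08 / (0.92 × 0.18)) = 0.63

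The chance that at least one z exceeds 1.96 in the NR direction is 6.4%, against 2.5% for one test. Two-sided it is 12.7% against 5%. Over the full range of event rates the figures are 5.9–6.8% and 11.7–13.6%. The independence bounds are 1 − 0.975³ = 7.3% and 1 − 0.95³ = 14.3%.

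**Step 2: how often the switch occurs.** The model has six covariate columns (treatment, age, gender, two for site, creatinine), so the global score test has 6 × (3 − 1) = 12 df. About 6,000 null trials per setting were simulated with no treatment effect. The log-scale correlation of baseline with AUC is s_b/√(s_b² + s_t²), where s_b and s_t are the assumed SDs of log baseline and of log change. SDs of 0.5 and 0.3 give 0.86; 0.5 and 0.5 give 0.71; 0.4 and 0.8 give 0.45. After a switch, treatment was freed at the three cutpoints and tested by Wald. N = 100, dialysis 10% and death 8% unless noted.

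| Setting | Switch | Any of three favouring NR, after switch | Single OR favouring NR, all trials | Whole procedure favouring NR | Whole procedure, two-sided |
|---|---|---|---|---|---|
| r ≈ 0.86 | 98% | 6.7% | 2.6% | 6.6% | 13.1% |
| r ≈ 0.71 | 76% | 6.7% | 2.9% | 5.9% | 12.1% |
| r ≈ 0.71, N = 80 | 64% | 6.0% | 2.6% | 4.9% | 9.8% |
| r ≈ 0.45 | 26% | 7.2% | 3.1% | 4.2% | 8.3% |
| AUC divided by baseline | 16% | 9.0% | 2.9% | 3.9% | 7.4% |
| No covariate effects | 4% | 8.8% | 3.0% | 3.3% | 6.2% |

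At r ≈ 0.71, other event rates (5%/5% and 15%/10%) give 74% and 77% switching. Monte Carlo error is about 0.3 points on the whole-procedure rates. It is larger for the after-switch column where few trials switch: in the last row about 258 trials, √(0.088 × 0.912/258) = 1.8 points.

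**Step 3: is creatinine the cause?** In the five N = 100 rows, a 2-df test on creatinine alone rejects in 100%, 94%, 40%, 23% and 5%. The same test on the other five columns rejects in 21%, 16%, 11%, 9% and 5%. Where switching is frequent, creatinine drives it.

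**Step 4: the alternative.** Using the single treatment odds ratio whatever the check shows gives 2.6–3.2% favouring NR (5.0–6.1% two-sided) in every setting, including those where creatinine breaks proportionality.

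**The case against.** The strongest reply is that the plan discloses all of this. Section 9.4.1 waives multiplicity correction, the trial is a pilot, the endpoint is secondary, and the consequence is only further study. Section 2.1 already has a looser rule, p < 0.2 on any one secondary outcome with no increase in harm; a single two-sided test at that level gives about 10% in the benefit direction. Any-of-three is also a legitimate way to test a joint null, since one odds ratio different from 1 makes that null false; only the adjustment is missing. This stands and limits the severity. It does not justify letting a covariate's non-proportionality choose the treatment test.

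The trigger can also be read as a treatment-only check, because 9.4.3 links proportional odds to the odds ratio that summarizes treatment. With a 2-df treatment-only check at 5%, the same large-sample method gives a whole-procedure rate of about 4% favouring NR (about 8% two-sided). Creatinine then plays no part, but some inflation remains.

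A reader might infer that the ordinal analysis as a whole roughly doubles its false-positive rate and that baseline creatinine will often set this off. The documents do not support that as a flat statement. The doubling applies once the switch has occurred or where switching is frequent, and the switch rate runs from 4% to 98% across assumptions the documents do not settle. Sections 2.1 and 3 speak of creatinine AUC benchmarked to baseline, while the 9.4.3 text for this endpoint does not, so that point is open. Two-sided rates also count results favouring placebo, on which this rule does not act.

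**Conclusion.** The point holds in conditional form. After the switch, the rule runs at about 6–7% in the benefit direction instead of 2.5% (about 12–13% instead of 5% two-sided). This follows from the text and depends little on event rates. Over the whole procedure the rate favouring NR is about 3–7%.

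That creatinine can trigger the switch while treatment is proportional also follows from the text, if the check covers all model terms. How often it does so is an assumption: 64–98% for an unbenchmarked AUC correlated at about 0.7 or more with baseline, and about 16–26% if the AUC is benchmarked or the correlation is about 0.45. The figures use the 9.4.3 categories. The endpoint column of Table 2 in section 3 instead lists AUC tertiles plus death, and these need reconciling. Severity is modest.

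**What to change.** In 9.4.3, base the p ≤ 0.05 rule on one test of treatment:

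- Keep the common treatment odds ratio as the test, and relax proportionality only for covariates that fail the check. State the threshold and that it is applied term by term.
- If treatment itself may be non-proportional, use the joint 3-df test of OR1 = OR2 = OR3 = 1, and state how benefit is judged, since that test has no direction (for example, the common odds ratio favours NR).
- Report the three treatment odds ratios with confidence intervals as description only.
- Say whether the AUC is benchmarked for this endpoint, and reconcile the 0.05 rule with the p < 0.2 criterion in section 2.1.

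One caution on the joint test: named in advance and always used, it holds 5% in large samples. If it is used only after treatment fails its own 2-df check, the two-step rate is 0.95 × 5% + P(q > 5.99 and q + z² > 7.81) = 4.75% + 3.05% = 7.8% two-sided. Here q is chi-square on 2 df and z² is an independent chi-square on 1 df. The plan should either name the joint test outright or accept and state that figure.

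The cost is a few sentences before unblinding, with no extra data. The trade-off is that a common odds ratio can hide a treatment effect that differs across cutpoints, which the descriptive odds ratios would still show.
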